4.0 PATIENT REGISTRATION

4.1 Investigator and Research Associate registration with CTEP

Food and Drug Administration (FDA) regulations require sponsors to select qualified investigators. National Cancer Institute (NCI) policy requires all individuals contributing to NCI-sponsored trials to register with their qualifications and credentials and to renew their registration annually. To register, all individuals must obtain a Cancer Therapy Evaluation Program (CTEP) credentials necessary to access secure NCI Clinical Oncology Research Enterprise (CORE) systems. Investigators and clinical site staff who are significant contributors to research must register in the Registration and Credential Repository (RCR). The RCR is a self-service online person registration application with electronic signature and document submission capability.

RCR utilizes six person registration types.

- Investigator (IVR) — MD, DO, or international equivalent;
- Non Physician Investigator (NPIVR) — advanced practice providers (e.g., NP or PA) or graduate level researchers (e.g., PhD);

- Associate Plus (AP) — clinical site staff (e.g., RN or CRA) with data entry access to CTSU applications such as the Roster Update Management System [RUMS], OPEN, Rave, acting as a primary site contact, or with consenting privileges;
- Associate (A) — other clinical site staff involved in the conduct of NCI-sponsored trials; and
- Associate Basic (AB) — individuals (e.g., pharmaceutical company employees) with limited access to NCI-supported systems.

RCR requires the following registration documents:

Documentation Required	IVR	NPIVR	AP	A	AB
CTEP-IAM Account with ID.me credentials	✓	✓	✓	✓	✓
FDA Form 1572	✓	✓			
• Practice sites, IRBs, and labs					
Financial Disclosure Form	✓	✓	✓		
NCI Biosketch (education, training, employment, certification, licensure, ABMS certification, GCP Training, personal statement, memberships, honors, publications, research support)	✓	✓	✓		
GCP Training Certificated (mandatory file upload)	✓	✓	✓		
Agent Shipment Form (if applicable)	✓				
CV (optional file upload)	✓	✓	✓		
Annual Re-registration	✓	✓	✓	✓	✓

IVRs, and NPIVRs must list all clinical practice sites and Institutional Review Boards (IRBs) covering their practice sites in RCR to allow the following:

- Addition to a site roster;
- Selection as the treating, credit, or consenting person in OPEN;
- Ability to be named as the site-protocol Principal Investigator (PI) on the IRB approval; and
- Assignment of the Clinical Investigator (CI) task on the Delegation of Tasks Log (DTL).

In addition, all investigators acting as the Site-Protocol PI (investigator listed on the IRB approval), consenting or treating investigator in OPEN, or as the CI on the DTL must be rostered at the enrolling site with a participating organization..

Refer to the [NCI RCR page](#) on the [CTEP website](#) for additional information. For questions, please contact the **RCR Help Desk** by email at [contact].

4.2 Cancer Trials Support Unit registration procedures

Permission to view and download this protocol and its supporting documents is restricted and is based on the person and site roster assignment housed in the Roster Maintenance application and in most cases viewable and manageable via the Roster Update Management System (RUMS) on the Cancer Trials Support Unit (CTSU) members' website.

This study is supported by the NCI CTSU.

IRB Approval:

As of March 1, 2019, all U.S.-based sites must be members of the NCI Central Institutional Review Board (NCI CIRB) in order to participate in Cancer Therapy Evaluation Program (CTEP) and Division of Cancer Prevention (DCP) studies open to the National Clinical Trials Network (NCTN) and NCI Community Oncology Research Program (NCORP) Research Bases. In addition, U.S.-based sites must accept the NCI CIRB review to activate new studies at the site after March 1, 2019. Local IRB review will continue to be accepted for studies that are not reviewed by the CIRB, or if the study was

previously open at the site under the local IRB. International sites should continue to submit Research Ethics Board (REB) approval to the CTSU Regulatory Office following country-specific regulations.

Sites participating through the NCI CIRB must submit the Study Specific Worksheet (SSW) for Local Context to the CIRB using IRBManager to indicate their intent to open the study locally. The NCI CIRB's approval of the SSW is automatically communicated to the CTSU Regulatory Office, but sites are required to contact the CTSU Regulatory Office at [contact] to establish site preferences for applying NCI CIRB approvals across their Signatory Network. Site preferences can be set at the network or protocol level. Questions about establishing site preferences can be addressed to the CTSU Regulatory Office by email ([contact]) or by calling [name].

Sites using their local IRB or REB, must submit their approval to the CTSU Regulatory Office using the Regulatory Submission Portal located in the Regulatory section of the CTSU website. Acceptable documentation of local IRB/REB approval includes:

- Local IRB documentation;
- IRB-signed CTSU IRB Certification Form; and/or
- Protocol of Human Subjects Assurance Identification/IRB Certification/Declaration of Exemption Form.

In addition, the Site-Protocol Principal Investigator (PI) (i.e., the investigator on the IRB/REB approval) must meet the following criteria for the site to be able to have an Approved status following processing of the IRB/REB approval record:

- Have an active CTEP status;
- Have an active status at the site(s) on the IRB/REB approval (applies to US and Canadian sites only) on at least one participating organization's roster;
- If using NCI CIRB, be active on the NCI CIRB roster under the applicable CIRB Signatory Institution(s) record;
- Include the IRB number of the IRB providing approval in the Form FDA 1572 in the RCR profile;
- List all sites on the IRB/REB approval as Practice Sites in the Form FDA 1572 in the RCR profile; and
- Have the appropriate CTEP registration type for the protocol.

4.2.1 Additional site registration requirements

Additional site requirements to obtain an approved site registration status include:

- An active Federal Wide Assurance (FWA) number;
- An active roster affiliation with the Lead Protocol Organization (LPO) or a Participating Organization (PO);
- An active roster affiliation with the NCI CIRB roster under at least one CIRB Signatory Institution (US sites only); and

Compliance with all protocol-specific requirements (PSRs).

4.2.2 Protocol specific requirements for A032002 site registration

IROC credentialing:

This is a study with a radiation and/or imaging (RTI) component and the enrolling site must be aligned to an RTI provider. To manage provider associations, access the Provider Association page from the Regulatory section on the CTSU members' website at <https://www.ctsu.org/RSS/RTFProviderAssociation>. Sites must be linked to at least one Imaging and Radiation Oncology Core (IROC) provider to participate on trials with an RTI component. Enrolling sites are responsible for ensuring that the appropriate agreements and IRB approvals are in place with their RTI provider. Only an individual with a primary role on a treating site

roster can update the provider associations, though all individuals at a site may view provider associations. To find who holds primary roles at your site, view the Person Roster Browser under the RUMS section on the CTSU members' website.

IROC Credentialing Status Inquiry (CSI) Form – this form is submitted to IROC Houston to verify credentialing status or to begin a new modality credentialing process.

To complete protocol-specific credentialing the RTI provider or enrolling site should follow instructions in the protocol to submit documentation or other materials to the designated IROC Quality Assurance (QA) center. Upon the IROC QA center approving the RTI provider for the study modality, IROC will automatically send the approval to the Regulatory and Roster Maintenance applications to comply with the protocol-specific requirement, unless otherwise noted at the bottom of the IROC Credentialing Approval notification. IROC will continue to copy the provider and/or enrolling site on modality approvals.

Upon site registration approval in the Regulatory application, the enrolling site may access Oncology Patient Enrollment Network (OPEN) to complete enrollments. If the study is using the IROC integration suite, the enrolling site will select their credentialed provider treating the subject in the OPEN credentialing screen and may need to answer additional questions related to treatment in the eligibility checklist.

4.2.3 **Downloading Site Registration Documents**

Download the site registration forms from the protocol-specific page located on the CTSU members' website. Permission to view and download this protocol and its supporting documents is restricted to institutions and its associated investigators and staff or on a participating roster. To view/download site registration forms:

- Log in to the CTSU members' website (<https://www.ctsu.org>);
- Click on *Protocols* in the upper left of the screen
 - Enter the protocol number in the search field at the top of the protocol tree; or
 - Click on the By Lead Organization folder to expand, then select Alliance, and protocol number *A032002*.

Click on *Documents*, *Protocol Related Documents*, and use the *Document Type* filter and select *Site Registration* to download and complete the forms provided. (Note: For sites under the CIRB, IRB data will load automatically to the CTSU.)

4.2.4 **Submitting regulatory documents**

Submit required forms and documents to the CTSU Regulatory Office using the Regulatory Submission Portal on the CTSU members' website.

To access the Regulatory Submission Portal log in to the CTSU members' website, go to the *Regulatory* section and select *Regulatory Submission*.

Institutions with patients waiting that are unable to use the Regulatory Submission Portal should alert the CTSU Regulatory Office immediately by phone or email: [name], or [contact] in order to receive further instruction and support.

4.2.5 **Checking site registration status**

Site registration status may be verified on the CTSU members' website.

- Click on *Regulatory* at the top of the screen;
- Click on *Site Registration*; and
- Enter the site's 5-character CTEP Institution Code and click on Go.
 - Additional filters are available to sort by Protocol, Registration Status, Protocol Status, and/or IRB Type.

Note: The status shown only reflects institutional compliance with site registration requirements as outlined within the protocol. It does not reflect compliance with protocol requirements for individuals participating on the protocol or the enrolling investigator's status with NCI or their affiliated networks.

4.3 Patient Registration Requirements

4.3.1 Informed consent

The patient must be aware of the neoplastic nature of his/her disease and willingly consent after being informed of the procedure to be followed, the experimental nature of the therapy, alternatives, potential benefits, side-effects, risks, and discomforts. Current human protection committee approval of this protocol and a consent form is required prior to patient consent and registration.

4.3.2 Patient questionnaire booklets

Patient-completed booklets should be downloaded prior to the pre-registration of any patients. These booklets can be downloaded from the CIRB Approved Documents tab on the CTSU website. Patient-completed booklets will only be available in English.

4.4 Patient Registration Procedures

The Oncology Patient Enrollment Network (OPEN) is a web-based registration system available on a 24/7 basis. OPEN is integrated with CTSU regulatory and roster data and with the LPOs registration/randomization systems or the Theradex Interactive Web Response System (IWRS) for retrieval of patient registration/randomization assignment. OPEN will populate the patient enrollment data in NCI's clinical data management system, Medidata Rave.

Requirements for OPEN access:

- Active CTEP registration with the credentials necessary to access secure NCI/CTSU IT systems;
- To perform enrollments or request slot reservations: Must be on an LPO roster, ETCTN Corresponding roster, or participating organization roster with the role of Registrar. Registrars must hold a minimum of an Associate Plus (AP) registration type;
- Have an approved site registration for the protocol prior to patient enrollment.

To assign an Investigator (IVR) or Non-Physician Investigator (NPIVR) as the treating, crediting, consenting, drug shipment (IVR only), or receiving investigator for a patient transfer in OPEN, the IVR or NPIVR must list the Institutional Review Board (IRB) number used on the site's IRB approval on their Form Food and Drug Administration (FDA) 1572 in the Registration and Credential Repository (RCR.). If a DTL is required for the study, the IVR or NPIVR must be assigned the appropriate OPEN-related tasks on the DTL.

Prior to accessing OPEN, site staff should verify the following:

- Patient has met all eligibility criteria within the protocol stated timeframes; and
- All patients have signed an appropriate consent form and Health Insurance Portability and Accountability Act (HIPAA) authorization form (if applicable).

Note: The OPEN system will provide the site with a printable confirmation of registration and treatment information. You may print this confirmation for your records.

Access OPEN at <https://open.ctsu.org> or from the OPEN link on the CTSU members' website. Further instructional information is in the OPEN section of the CTSU website at <https://www.ctsu.org> or <https://open.ctsu.org>. For any additional questions, contact the CTSU Help Desk at [name] or [contact].

4.5 Registration to substudies and companion studies

4.5.1 Registration to Substudies described in [Section 14.0](#)

There is 1 substudy within Alliance A032002. This correlative science study must be offered to all English-speaking patients enrolled on Alliance A032002 (although patients may opt to not participate). This substudy does not require separate IRB approval. The substudies included within Alliance A032002 are:

- Quality of Life, Alliance A032002-HO1 ([Section 14.1](#))

If a patient answers “yes” to “I choose to take part in the Quality of Life study and will fill out these forms,” Question #1 in the model consent, they have consented to participate in the substudy described in Section 14.1. The patient should be registered to Alliance A032002-HO1 at the same time they are registered to the treatment trial (A032002). Questionnaires should be submitted per [Section 14.1](#).

4.6 Stratification Factors and Treatment Assignments

4.6.1 Stratification Factors

1) Platinum Status: Ineligible vs. Refractory

- Platinum ineligible is defined as meeting any one of the following criteria: Impaired renal function [creatinine clearance (CrCl) of <30 mL/min], >2 peripheral neuropathy, or NYHA Heart Failure of >3.
- Platinum-refractory is defined as prior platinum-based perioperative chemotherapy within 12 months of relapse or prior platinum-based chemotherapy for metastatic disease.

2) Visceral Metastasis: Yes vs. No

4.6.2 Treatment Assignments

Patients will be randomized 1:1 to the two treatment arms. The factors defined in [Section 4.8.1](#) will be used as stratification factors.

After the patient has been registered into the study, the values of the stratification factors will be recorded, and the patient will be randomized to one of the following treatment groups using the Pocock and Simon dynamic allocation procedure which balances the marginal distributions of the stratification factors between the treatment groups.

- 1) Immunotherapy
- 2) Immunotherapy + Single Site Radiotherapy

5.0 STUDY CALENDAR

Pre-study Testing Intervals

The pre-study testing intervals are guidelines only. Laboratory and clinical parameters during treatment are to be followed using individual institutional guidelines and the best clinical judgment of the responsible physician. It is expected that patients on this study will be cared for by physicians experienced in the treatment and supportive care of patients on this trial.

When calculating days of tests and measurements, the day a test or measurement is done is considered Day 0. Therefore, if a test were done on a Monday, the Monday one week later would be considered Day 7.

To be completed ≤ 28 DAYS before registration: All laboratory studies, history and physical.

To be completed ≤ 42 DAYS before registration: Any X-ray, scan of any type or ultrasound which is utilized for tumor measurement per protocol.

To be completed ≤ 60 DAYS before registration: Any baseline exams used for screening, or any X-ray, scan of any type or ultrasound of uninvolved organs which is not utilized for tumor measurement.

	Prior to Registration*	Day 1 of each cycle*	Post-treatment follow up**	At PD, withdrawal, or removal**
Tests & Observations				
History and physical, weight, PS***	X	X	X	X
Pulse, Blood Pressure	X	X		
ECG	X(6)			
Adverse Event Assessment-CTCAE		X	X	
Adverse Event Assessment-PRO-CTCAE	X(1)	X(1)	X	
Registration Fatigue/Uniscale Assessment	X(2)			
Laboratory Studies				
Complete Blood Count, Differential, Platelets	X	X		
Serum Creatinine	X	X		
Albumin, glucose	X	X		
AST, ALT, Alk. Phos., Bili	X	X		
TSH with reflex T4		X		
Serum or Urine hCG	X(3)			
UPC ratio/urine protein	X	A		
Staging				
Tumor Measurement	X	C	X	
CT chest/abd/pelvis	X(5)	D	D	
Correlative studies				
QOL assessment	From baseline through 24 months, see Section 6.5 .			
Tissue, blood, and urine samples	See Section 6.2 .			

- * Labs completed prior to registration may be used for day 1 of cycle 1 tests if obtained \leq 14 days prior to treatment. For subsequent cycles, labs, scans, tests and observations may be obtained \leq 72 hours prior to day of treatment.
- ** Physical examination and staging scans are required \leq 12 weeks after the end of treatment, then every 12 weeks until disease progression; thereafter, survival information is required every 3 months until 3 years following registration. See also Section 12.0.
- *** Patients receiving immunotherapy will be assessed for pulmonary signs and symptoms throughout the study.
 - 1 The PRO-CTCAE assessment is required for all patients. If the PRO-CTCAE assessment completed prior to registration is obtained \leq 14 days prior to treatment, then the PRO-CTCAE assessment on day 1 of cycle 1 may be skipped. The PRO-CTCAE patient-completed booklet for this protocol can be found on the 'CIRB Approved Documents' tab on the CTSU website.
 - 2 To be completed after registration and \leq 21 days prior to treatment.
 - 3 For women of childbearing potential. Must be done \leq 14 days prior to initiation of study treatment.
 - 4 See Section 6.2.

- 5 Baseline scans can include either: 1) a CT, spiral CT, or MRI and bone scan, or 2) an FDG-PET scan and diagnostic CT performed with both IV and oral contrast, and the CT acquired with 5 mm or less slice thickness. Supporting documentation is to be submitted, per Section 6.1.1.
- 6 ECG prior to registration should be performed if clinically indicated.
 - A All patients receiving immunotherapy will have a urinalysis or urine protein performed \leq 72 hours prior to every dose. If urine protein is \geq 2+, 24-hour urine collection or UPC ratio will be required.
 - B Required only if signs or symptoms suggestive of metastases develop.
 - C \leq 2 days prior to each treatment if accessible to physical examination.
 - D Every 3 months until evidence of progression or relapse. If the baseline scans were a CT or MRI and bone scan, follow-up bone scans are required only for patients with bone metastases as the only site of evaluable disease, and are optional for other patients. Response assessment should include assessment of all sites of disease and use the same imaging method as was used at baseline. Bone imaging (after baseline) is required only if indicative of metastases at baseline or if signs or symptoms suggestive of metastases develop.

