6.4.1 Detailed Steps of Data Submission

Collection of images is required. Alliance A032002 prescribes limited image acquisition requirements, so any imaging acquired is expected to be done per protocol rather than the site's own standard of care. Specifically, PET/CT, CT, MRI and bone scans must be acquired at the following times and subsequently submitted. Supporting documentation must accompany all submissions for this trial. Images will be collected digitally for central archiving and curation. Imaging studies will be collected digitally at the following time points:

1. Baseline – within 42 days before registration
 - a. CT of the chest/abdomen/pelvis
 - i. Intravenous and oral contrast unless contraindicated
 - ii. 5mm of less slice thickness
 - b. Substitutions allowed:
 - i. CT of the chest and MRI of the abdomen/pelvis
 1. Must be diagnostic quality
 2. Intravenous and oral contrast unless contraindicated
 3. 5mm or less slice thickness
 - ii. FDG-PET/CT of the whole body or limited whole body
 1. CT must be of diagnostic quality
 2. Intravenous and oral contrast unless contraindicated
 3. 5mm or less slice thickness
 - c. Bone scan of the whole body
2. Restaging – every 3 months +/- 14 days
 - a. Same imaging as acquired at baseline
 - b. Bone imaging only required if indicative of metastases at baseline or if signs or symptoms develop
3. Progression

4. Confirmatory Follow-up – 12 weeks after evidence of objective response

The complete imaging data set in digital DICOM format will be submitted electronically to the Imaging and Radiation Oncology Core at Ohio (IROC Ohio) within no more than 3 business days upon the image acquisition completeness. BMP files, JPG files, or hard copies (films) are not acceptable. The raw data of the entire study should be saved until the imaging data is accepted by IROC Ohio.

If not using TRIAD, sites need to de-identify the patient data using institutional procedures to remove patient name and medical record number while preserving the Alliance patient ID number (e.g., 112136) and protocol number (e.g., ALLIANCE032002), respectively.

DICOM tag dates and times cannot be altered prior to submission as they are used to put submissions into context regarding patient treatment. Additional changes to DICOM tags prior to submission impede further technical analysis and should be avoided whenever possible.

Imaging data should be submitted electronically to IROC Ohio via TRIAD, Web Transfer or FTP Transfer:

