7.1 Immunotherapy with Pembrolizumab

Protocol therapy will consist of 1 cycle administered every 21 days. Treatment will continue until disease progression and no longer benefiting clinically, or unacceptable adverse event. Treatment may continue beyond disease progression per iRECIST guidelines. That is, treatment may continue beyond assessment of progressive disease (PD) provided the patient is clinically stable and felt to be continuing to benefit from therapy. A patient may be deemed clinically stable provided that no worsening of performance status has occurred, there have been no clinically relevant increases in disease-related symptoms such as pain or dyspnea that are thought to be associated with disease progression, and there has been no requirement for intensified management of disease-related symptoms, including increased analgesia, radiotherapy, or other palliative care. Repeat imaging should be obtained within 4-8 weeks if feasible, and no later than 3 months. If the subsequent scan shows additional new lesions or increase in new lesion size (sum of measurements \geq 5 mm), treatment should be discontinued.

Arm	Agent	Dose	Route	Day	Rx
A	Pembrolizumab	200 mg	IV*	Day 1	Every 3 weeks
B	Pembrolizumab + RT	200 mg + RT**	IV*	Day 1	Every 3 weeks***

* Infused over approximately 30 minutes (range: 25-40 minutes).

** Patients will receive 3 fractions of radiation to a total dose of 24 Gy (8 Gy x 3 fractions).

Administration of radiotherapy will occur to a single site for subjects randomized to the pembrolizumab and radiotherapy group.

***Radiotherapy can be initiated after the first dose of immunotherapy and must be completed before 12 weeks after first dose of immunotherapy administered.

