After initial progression (iUPD) but then iCR, iPR, or iSD	Any PD precludes later CR, PR, or SD	iCR/iPR/iSD can be achieved after initial iUPD. Sum of target lesion diameters at time of iCR/iPR/iSD should be noted and status should be reset. Subsequent progression after iCR/iPR/iSD should be another iUPD, until confirmation iCPD
New lesions	Result in PD; recorded but not measured	Results in iUPD at first occurrence iCPD only assigned on basis of new lesions if at next assessment additional new lesions appear or an increase in size of new lesions seen (>5mm of sum of new lesion target or any increase in new lesion non-target) If non-target or target lesions have unequivocal PD, iCPD can be assigned at time of first progression
Independent blinded review and central scan collection	Collection of scans required on A031704	Collection of scans required on A031704
Confirmation of progression	Not required unless equivocal	Required
Consideration of clinical status	Not included in assessment	Clinical stability is considered when deciding whether treatment should continue after iUPD

In general, iRECIST guidelines help define progression in the context of immune therapy. New lesions should be assessed and subcategorized as target lesions (new lesion, target) and measured for further follow up, or non-target lesions (new lesion, non-target). At the time of initial iUPD, patients must be clinically stable by investigator assessment (see definition below) in order to continue immunotherapy-based treatments. iRECIST guidelines also recommend that confirmation of progression be obtained between 4 to 8 weeks of the initial iUPD scan date. For purposes of this trial, these scans can be obtained after 4 weeks, and no more than 13 weeks after initial iUPD scans (as standard of care, depending on insurance coverage, as scans will not be billable to this study).

Investigators will need to assess clinical stability to continue treatments at time of iUPD. Clinical stability to continue treatment in light of iUPD is defined as follows. Absence of any of the following:

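### The repeat scan after first progression, on which the central iRECIST endpoint depends, is requested in Sections 7.1 and 11.7 but is missing from the calendar and not named for central submission

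*Combined protocol and SAP*

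**What the plan says.** Rules that end scanning at progression:

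- Section 5.0, footnote D, schedules CT "Every 3 months until evidence of progression or relapse".
- The double-asterisk note to the same calendar, repeated in Section 12.3.1, requires scans after treatment "then every 12 weeks until disease progression; thereafter, survival information is required every 3 months until 3 years following registration".
- None of these rules separates unconfirmed progression (iUPD) from confirmed progression (iCPD).

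Rules that ask for a scan after first progression:

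- Section 7.1, for patients treated beyond progression: "Repeat imaging should be obtained within 4-8 weeks if feasible, and no later than 3 months".
- Section 11.7: "these scans can be obtained after 4 weeks, and no more than 13 weeks after initial iUPD scans". The same sentence treats the scans as standard of care, subject to insurance and not chargeable to the study. The 11.7 table marks confirmation of progression as required under iRECIST.

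Rules on central submission:

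- Section 6.4.1 lists baseline, "Restaging – every 3 months +/- 14 days", progression, and "Confirmatory Follow-up – 12 weeks after evidence of objective response". No item names a scan after iUPD.
- Section 6.4.1 also says that "any imaging acquired is expected to be done per protocol rather than the site's own standard of care".
- The 11.7 table row on central scan collection says collection is required, but cites A031704 rather than A032002.

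Use of the scans: Section 13.2.2 defines iRECIST response by central review, and Section 13.7 makes it a key secondary analysis that repeats the primary one. Section 1.1 lists a result positive by iRECIST among three envisioned outcomes of the trial.

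**The concern.** By the protocol's own comparison table, measurability and the confirmation of CR and PR are the same under iRECIST and RECIST 1.1. For response, what iRECIST adds is that a patient may still reach iPR or iCR after iUPD. That can be seen only on a scan taken after iUPD, and the endpoint counts it only if the central reviewer receives it.

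A site can follow the calendar, Section 12.3.1 and the submission list to the letter and still omit that scan. Whether it exists then depends on three things outside the assessment schedule: the site's reading of the protocol, the patient's insurance, and the investigator's judgement that the patient is stable and benefiting. The third is made with the arm known, so capture could differ between arms and shift the comparison as well as thin it out. The iRECIST result could lead to a phase 3 trial with iRECIST response as its primary endpoint, so it deserves a defined set of images.

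**Working it through.** **1. The plan's own figure.** Inputs from Section 13.4: one-sided alpha 0.10, power 90%, response 20% against 40%, allocation 1:1. With pooled variance and no continuity correction, n per arm = [1.2816·√(2·0.30·0.70) + 1.2816·√(0.20·0.80 + 0.40·0.60)]² / 0.20² = [1.2816·(0.648 + 0.632)]² / 0.04 ≈ 67.3, rounded up to 68. The total is 136, and 136/0.95 = 143.2 gives 144. The stated figures reproduce, with power 90.2% at 68 per arm. Nothing in this point changes them.

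**2. What each provision does for a patient with iUPD who stays on treatment.**

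| Provision | Scan after iUPD |
|---|---|
| 5.0, footnote D and double-asterisk note; 12.3.1 | Not scheduled: scans end at progression |
| 7.1 | Requested, 4-8 weeks if feasible, 3 months at most |
| 11.7 text | Allowed from 4 to 13 weeks, outside study billing |
| 11.7 table | Confirmation required; scan collection required, under A031704 |
| 6.4.1 | Not named; the restaging item has no written stop |

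A patient with iUPD who is clinically unstable stops study treatment (Section 11.7), and no later scan is scheduled.

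**3. Do the windows in 7.1 and 11.7 agree?** Both prefer 4-8 weeks. Three months is 365.25/4/7 = 13.0 weeks, so the outer limits agree too.

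**4. Could the scan fall inside 6 months?** Section 13.2.2 gives no time window for iRECIST response. I infer 6 months (365.25/2/7 = 26.1 weeks) because Section 13.7 repeats the primary analysis.

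- First progression at week 12 ± 2, plus at most 13 weeks, gives week 23 to 27. Plus 8 weeks, it gives week 18 to 22.
- Weeks count from the first dose. Treatment may start up to 14 days after registration (Section 7.0), which can add up to 2 weeks: 24 at most for the 8-week limit, 29 for the 13-week limit.
- First progression at week 24 leaves 26.1 − 24 = 2.1 weeks, less than the 4-week minimum, so a later response would fall outside.

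For most patients who progress at the first scan, one repeat scan therefore fits, if it is done and sent.

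**5. Size.** The documents give no rate of response after iUPD, so all such rates here are assumed. One responder in 68 is 1/68 = 1.5 points. At 2 to 10%, 0.02·68 = 1.4 and 0.10·68 = 6.8, so about 1 to 7 patients per arm if none is captured.

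Power of the iRECIST comparison, by the formula of step 1 at 68 per arm (unstratified approximation):

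| RECIST response, A vs B | Added after iUPD, A vs B | No capture | Half | Full |
|---|---|---|---|---|
| 20% vs 40% | 3% vs 10% | 90.2% | 95.4% | 98.1% |
| 20% vs 30% | 3% vs 10% | 52.6% | 68.2% | 80.7% |
| 20% vs 30% | 2% vs 5% | 52.6% | 59.3% | 65.6% |
| 20% vs 40% | 5% vs 5% | 90.2% | 89.2% | 88.3% |

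With equal rates in both arms, capture adds no power.

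**6. Unequal capture.** If the true rate after iUPD is r in both arms and the captured fractions are c_A and c_B, the observed difference moves by r·(c_B − c_A). With r = 5%, full capture in one arm and half in the other, that is 0.05·0.5 = 2.5 points, or 1.7 patients in 68.

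**The case against.** The strongest reply is that the protocol already provides for this scan. Section 7.1 says it should be obtained, Section 11.7 marks confirmation of progression as required, and Section 12.2 ends treatment on progression by iRECIST. In Section 6.4.1 the restaging item has no written stop and the progression item is not limited to first progression, so a repeat scan could be submitted under either. Section 11.0 orders re-evaluation every 12 weeks, also without a stop. The 11.7 table requires scan collection, with what looks like a wrong study number carried over. The separate Data Submission Schedule is not among the documents and may say more. Stopping at first progression also suits PFS, which is defined by RECIST 1.1.

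Much of this stands, and it rules out stronger readings:

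- A reader might infer that the endpoint cannot capture responses after iUPD, or that central iRECIST must collapse into RECIST 1.1. The documents do not support that: patients kept on treatment are the ones in whom a late response could be seen, and Sections 7.1 and 11.7 call for their scan.
- A reader might infer that nothing sends the scan to central review. The open restaging item and the table row speak against that.
- A reader might infer that the windows in 7.1 and 11.7 conflict. They agree, as step 3 of the working shows.

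The reply does not remove the mismatch. The calendar and Section 12.3.1 end scans at progression without qualification, the submission list needs a generous reading, and an insurance-dependent scan sits badly with the expectation in 6.4.1 that imaging follow the protocol and not local standard of care.

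**Conclusion.** The point holds as an unreconciled inconsistency that makes a key secondary endpoint unreliable. It does not make the endpoint impossible to assess. Capture of responses after iUPD depends on site, insurance and the decision to continue treatment, and it could differ by arm. That a difference would occur is not shown by the documents; the open-label design only makes it possible.

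The figure of about 1 to 7 responders per 68 is an upper bound on what is at risk, not an expected loss. It rests on the assumed 2 to 10% rate, on zero capture, and on counting a patient without a later scan as a non-responder. Some late responses would miss a 6-month window whatever the wording. The power figures are illustrations: they matter most if the RECIST difference is modest and late responses favour Arm B, and not at all if late rates are equal. The primary RECIST 1.1 endpoint, its sample size and PFS are untouched. The change should be made, but the primary analysis does not depend on it.

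**What to change.** - Reconcile Section 5.0 (footnote D and the double-asterisk note), 6.4.1, 7.1, 11.7 and 12.3.1, so that for patients treated beyond iUPD the calendar carries the repeat scan that 7.1 and 11.7 already request. PFS can stay as defined.
- Add a repeat scan after iUPD as a named item in the 6.4.1 submission list.
- Correct A031704 to A032002 in the 11.7 table.
- Report by arm the number of patients with iUPD, split into those with and without a centrally reviewed scan after it, so that unequal capture is visible.

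The cost is amendment wording and extra uploads of scans already requested. One item needs a decision: a scan carried in the calendar must be squared with the statement in 11.7 that it is not billable to the study. No new scans are proposed for patients who have stopped treatment; for them the by-arm count shows the gap.
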